10.0 Statistical Considerations

The primary endpoint is time to achieve complete re-epithelialization. The mean number of days required to achieve complete re-epithelialization between control and experimental groups will be analyzed with a Student's T-test. The null hypothesis is that there is no statistically significant difference between control and experimental complete re-epithelialization times. Secondary outcomes of patient and observer cosmetic outcome will be compared similarly.

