The novel biomaterial APIS[®] (SweetBio, Inc. Memphis, TN) is an advanced synthesis of gelatin, manuka honey, and hydroxyapatite bioengineered to protect wounds, manage exudate, and maintain a moist environment. It is FDA cleared (FDA number K1827250) for wound management across 9 indications including surgical wounds. It has been used successfully in a small case series of 8 patients for post-operative Mohs surgical wounds on the head and distal lower extremities. Time to complete re-epithelialization was 6 weeks (42 days), suggesting a reduction in healing time compared to standard SIH times for the leg and head of 127 and 57 days, respectively.^{10,11} Use of this novel biomaterial to enhance SIH is hypothesized to reduce healing times when compared to standard SIH wound care. This provides a useful option to aid SIH in sites like the lower legs, where healing can be prolonged due to intrinsic factors (e.g., cardiovascular disease, peripheral vascular disease, diabetes) or extrinsic factors (e.g., increased risk of surgical site infection following dermatologic surgery at sites below the knee).^{10,12}

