6.0 Study Procedures

Arms and Interventions Two experimental groups

- 1) APIS[®] biomaterial on the head
- 2) APIS[®] biomaterial on the distal lower extremities

Two control groups

- 1) No intervention, standard SIH wound care on the head
- 2) No intervention, standard SIH wound care on the distal lower extremities

Experimental (40 patients): APIS[®] biomaterial. APIS[®] biomaterial placed on post-operative wound.

- 1) Head (20 patients)
- 2) Distal lower extremities (20 patients)
 - a. Device: APIS[®] biomaterial. This biomaterial was FDA cleared in 2019 for management of full and partial thickness wounds, pressure ulcers, venous stasis ulcers, diabetic ulcers, surface wounds, traumatic wounds, surgical wounds, abrasions, and donor site wounds.
 - b. One layer of APIS[®] will be applied to the post-operative wound covered by petrolatum impregnated gauze, a non-stick Telfa pad, gauze, and Opsite tape.

c. The biomaterial will be reapplied if it is completely absorbed at follow up and the wound depth below the epithelial level.

No intervention (40 patients): No APIS[®] biomaterial on post-operative wound.

- 3) Head (20 patients)
- 4) Distal lower extremities (20 patients)
 - a. Post-operative wound will heal via conventional secondary intention. Application of petrolatum impregnated gauze, a non-stick Telfa pad, gauze, and Opsite tape.

This study may be deemed complete prior to reaching above enrollment numbers if statistical significance is achieved or at the discretion of the research team.

Mohs Surgery – Day 0

Patients eligible for study will be offered opportunity to enroll. After informed consent has been obtained, the patient's clinical history, medical history, social history, medication history, and vital signs will be reviewed and documented. Pre and postoperative photos will be obtained and stored in the Electronic Medical Record and Vanderbilt HIPAA compliant Box.

Patients on day of surgery will be provided with a post-operative wound care instruction sheet (for both control and experimental groups). They will also receive a detailed instruction sheet for uploading post-operative photos to Vanderbilt's HIPAA compliant Box.

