Subsequent Post-operative Visits – Post operative Day 14 then every 14 days thereafter until complete re-epithelialization is achieved. Patients enrolled in study will be provided a brief questionnaire to complete at in-person office follow-up visits. Post-operative wounds will be assessed for any complications. Size of wounds in addition to photographs will be obtained until complete re-epithelialization is achieved. Patients will also upload post-operative photos to Vanderbilt's HIPAA compliant Box post-operative day 7 then every 14 days thereafter until complete re-epithelialization is complete.

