9.0 Study Withdrawal/Discontinuation

Participants have the ability to withdraw or discontinue from the study at any time. Subjects will be instructed to notify a member of the study team if they wish to withdraw, and any data collected for research will be discarded.

Participants enrolled in the study may be terminated from the study at the investigator's discretion including but not limited to the following:

- Lost to follow-up
- Nonadherence with wound care
- A participant's health status changes significantly which makes them not eligible for the study
- Trauma to the post-operative wound

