11.0 Privacy/Confidentiality Issues

All data will be secured, and confidentiality will be upheld by all members of the research team. Participants will be assigned a study identification code in order to deidentify the study data. A crosslink will exist to link study identification codes to participant identifiers. This crosslink will only be accessible to a limited number of IRB trained and approved study personnel. Study data will be contained in a password protected Excel spreadsheet and stored on the Vanderbilt HIPAA compliant Box. Patients enrolled in this study may request to have all data removed/destroyed from the database if they elect to withdraw from the study.

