12.0 Follow-up and Record Retention

Study duration expected to be 12 months. Study data will be maintained by the research team for a minimum of 7 years and potentially indefinitely. This data will continue to be stored in a password protected database file on the Vanderbilt HIPAA compliant Box, in compliance with Vanderbilt University Medical Center's record retention policies. A limited number of IRB trained, and approved study personnel will have access.

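### The primary t-test on mean days to healing has no place for wounds not seen to heal, so the estimated saving in days is biased whenever follow-up is incomplete

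*Combined protocol and SAP*

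**What the plan says.** The primary endpoint is the number of days from surgery to full re-epithelialization (section 2.0). Section 10.0 analyses it in one sentence: "The mean number of days required to achieve complete re-epithelialization between control and experimental groups will be analyzed with a Student's T-test".

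Sections 2.0 and 6.0 intend follow-up to healing, with visits at day 14 and then "every 14 days thereafter until complete re-epithelialization is achieved". Patient photos fall in the alternate weeks, so healing is observed on a grid of about 7 days.

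Other sections allow a patient to leave without an observed healing day:

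- Section 9.0: a participant may withdraw at any time, and "any data collected for research will be discarded". The investigator may also terminate participation; the listed reasons include "Lost to follow-up", poor adherence to wound care, changed health and wound trauma.
- Section 11.0: participants who withdraw "may request to have all data removed/destroyed from the database".
- Section 6.0: "This study may be deemed complete prior to reaching above enrollment numbers if statistical significance is achieved", or at the team's discretion.
- Section 12.0: "Study duration expected to be 12 months". Section 1.0 cites "standard SIH times for the leg and head of 127 and 57 days, respectively".

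No section mentions censoring, a survival method, an analysis population, missing data or a value for an unhealed wound.

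**The concern.** A wound without a healing day cannot enter a t-test of mean days. With no rule to keep it, the analysis becomes a comparison of means among wounds seen to heal (healed-only below). A slow wound is exposed longer to loss, termination and study close, so the wounds left out are mostly the slow ones.

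If both arms face the same close date or loss rate, the slower arm loses more of its long times. Its mean is shortened more, and a real benefit is understated. If loss differs between arms, the bias can go either way and can create a difference where there is none. The trial's main result, the days saved by the biomaterial, would then depend partly on how patients were accrued and retained.

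**Working it through.** The plan gives no power calculation, spread, accrual period or loss rate, so it has no figure of its own to reproduce and the result is a range.

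**Inputs from the plan.** Control times 57 days (head) and 127 days (leg); biomaterial 42 days (case series of 8, both sites together); 20 patients per arm and site; 12 months.

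**Assumptions.** Lognormal times with CV 0.5 (0.3 and 0.7 as checks); the cited times taken as means; sites pooled; two-sided 5% test; healing seen on a 7-day grid in the simulations; loss unrelated to healing. The head ratio 42/57 = 0.737, a 26% reduction, is also applied to legs.

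**True difference.** The pooled control mean is (57 + 127)/2 = 92 days. The difference is 92 × (1 − 0.737) = 24.2 days. If the biomaterial takes 42 days at both sites, it is 92 − 42 = 50 days.

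**Formula.** Let G(t) be the probability of still being under follow-up at day t. The share seen to heal is E[G(T)] and the healed-only mean is E[T·G(T)]/E[G(T)], with numerator and denominator each summed over the two sites. If G = 1 throughout, there is no bias.

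**Close at 12 months, no other loss.** Follow-up is uniform between 365 days minus the accrual period and 365 days. Two checks on the control leg:

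- Entry at start: log-scale SD = √ln(1.25) = 0.472 and log-mean = ln 127 − 0.112 = 4.733, so P(T > 365) = P(Z > (5.900 − 4.733)/0.472) = P(Z > 2.47) = 0.7%.
- 12-month accrual: the unhealed share is about E[T]/365 = 127/365 = 34.8%.

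| Accrual | Control-leg wounds unhealed | Healed-only difference (true 24.2) | Healed-only difference if 42 days at both sites (true 50) |
|---|---|---|---|
| All at start | 0.7% | 23.2 | 49 |
| 6 months | 4.7% | 20.6 | 45 |
| 9 months | 15.5% | 18.1 | 40 |
| 12 months | 34.7% | 17.8 | 38 |

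From entry at start to 12-month accrual, the 24.2-day case runs from 24.2 to 20.4 with CV 0.3 and from 20.9 to 15.3 with CV 0.7.

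**No close date, equal loss.** G(t) = (1 − p)^(t/90). For p = 20%, 0.8^(127/90) = 0.73, so about 27% of control-leg wounds are not seen to heal. For p = 5, 10 and 20% the shares are 7, 14 and 27%, and the healed-only differences are about 23, 22 and 20.8 days.

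**No close date, unequal loss (20% v 5% per 90 days).** With no true effect, the healed-only means differ by about 6 days in favour of the arm with more loss. With the 26% effect, the estimate is 26.5 days if more is lost on the biomaterial and 17.3 days if more is lost on control. A milder imbalance (20% v 10% per 100 days) gives about 2 to 4 days under no effect.

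**Power for the 26% effect** (4,000 simulated trials per scenario, Monte Carlo SE under 0.8 points):

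| Scenario | Healed-only t-test | Healed-only, adjusted for site | Site-stratified log-rank |
|---|---|---|---|
| No censoring | 54% | 72% | 74% |
| 12-month close, 6-month accrual | 47% | 69% | 74% |
| 12-month close, 9-month accrual | 43% | 66% | 76% |
| 12-month close, 12-month accrual | 34% | 60% | 69% |
| 20% equal loss, no close | 41% | 62% | 68% |

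The step from the first to the second method, 18 to 26 points, comes from accounting for site. The step to the survival method adds 2 to 10 points. If the biomaterial takes 42 days at both sites, power is near 100% by any method.

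**Type I error.** The plain t-test rejects in 0.9 to 2.3% of null trials with equal censoring and 2.7 to 4.2% with unequal loss. It is conservative because site variation stays in its error term. The stratified log-rank rejects in 4.9 to 6.5% and 4.9 to 5.6%.

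**Does keeping open wounds as censored help?** Simulations with a 25% reduction (true difference 0.25 × 92 = 23 days), a 12-month close, 9- or 12-month accrual and several loss patterns gave healed-only differences of 13.9 to 17.0 days. The Kaplan-Meier restricted mean difference to 180 days was 19.1 to 19.5, against a true restricted value of 19.0 to 19.5.

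**The case against.** The strongest reply is that the protocol follows each wound until it heals, with no stated maximum, and that an expected duration is not a close date. Data are expressly discarded only for withdrawals; for patients lost, terminated or still open at the end, exclusion is inferred from the lack of any rule. This stands as a condition: with complete follow-up the bias is zero. It does not remove the point, because section 9.0 itself anticipates loss, and equal loss biases the estimate without any close date.

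The largest figures also need a harsh reading, with patients enrolled up to the last day of a hard 12-month cut. The 34.7% is the worst cell; across all controls it is about 25%, and about 2.4% with 6-month accrual.

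Part of the pooled bias is a shift in site mix rather than censoring within site. Averaging the two within-site differences gives about 19.5 days instead of 17.8 at 12-month accrual, and about 4 days instead of 6 under unequal loss with no effect. Section 10.0 does not say whether sites are pooled. On the head alone the bias is small: 15.0 falls to 13.7 days at worst under the 12-month close.

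Finally, a Cox model assumes proportional hazards, which the lognormal model used here does not satisfy, and a hazard ratio loses the scale of days. This bears on how the effect is reported, not on the need to keep open wounds in the analysis.

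**Conclusion.** The concern holds. The planned test requires a healing day for every patient, the plan creates patients without one, and nothing in it keeps them in the analysis.

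Under the central assumptions, the estimate falls short of a true 24.2 days by 1.0 to 6.4 days with a 12-month close, and by about 1 to 3.4 days with equal loss of 5 to 20% per 90 days. Unequal loss can move it by several days in either direction. With complete follow-up there is no bias. Spread, accrual, loss and the leg effect are all assumed.

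This is a problem of estimation and, to a lesser degree, power. It is not one of false positives: type I error was not inflated in any scenario run. Most of the power gap seen with the plain t-test comes from ignoring site. The primary analysis should be changed before the data are analysed.

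**What to change.** Replace the primary analysis in section 10.0 with text such as:

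> Time from surgery to complete re-epithelialization will be analysed in all randomised patients, in the arm assigned, with Kaplan-Meier curves and a log-rank test stratified by site (head or distal lower extremity). The effect will be given as a site-stratified Cox hazard ratio with 95% CI, and as median days by arm and site. Wounds not seen to heal will be censored at the last assessment (visit or photo). The number of censored wounds and the reasons will be reported by arm and site, because the analysis assumes censoring unrelated to healing prognosis.

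Reword sections 9.0 and 11.0:

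> Data collected up to withdrawal or termination will be kept and analysed where consent allows. The number of participants whose data are removed on request will be reported by arm.

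Two additions are worth considering. A restricted mean difference to a pre-set day keeps the result in days and does not need proportional hazards. An interval-censored sensitivity analysis would use the visit and photo dates directly.

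The cost is one statistics paragraph and small edits to the withdrawal, confidentiality and matching consent wording, with no new visits or data. The headline becomes a hazard ratio and medians unless the restricted mean is added. The result also rests on non-informative censoring: terminations for poor adherence, changed health or wound trauma may be related to prognosis, and a survival method does not fully correct for that.

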2.0 Rationale and Specific Aims

Randomized, comparative studies evaluating augmented SIH compared to conventional SIH in dermatologic surgery are limited. This study aims to evaluate whether use of a novel biomaterial enhances SIH, particularly in shortening time to complete re-epithelialization. Patients undergoing Mohs micrographic surgery amenable to SIH on the head and distal lower extremities will be randomized into one of four groups (standard SIH or biomaterial APIS[®] enhanced SIH on the head or distal lower extremities). Patients will have regularly scheduled follow-up with questionnaires at each visit. We aim to evaluate whether use of this novel biomaterial decreases complete reepithelialization times, reduces infection rates, and improves cosmetic outcomes.

Outcome Measures

Primary:

1. Time to complete re-epithelialization

Patients will be seen in office 14 days post-operative, then every 14 days thereafter until complete re-epithelialization is achieved. Patients will also submit photos via Vanderbilt HIPAA compliant Box at regular follow-up intervals (post-operative day 7 then every 14 days thereafter until complete re-epithelialization is achieved). Time elapsed from surgery date to complete re-epithelialization will be noted in days.

Secondary:

1. Patient and Observer Scar Assessment Scale (POSAS) Patient Scale Score Version 2.0

Patients will complete the POSAS Patient Scale after complete re-epithelialization is achieved. The POSAS Patient Scale is a validated and widely accepted scar assessment tool. The patient scale has six questions assessing scar pain, itch, color, stiffness, thickness, and irregularity rated from 1 (no, not at all/normal skin) to 10 (yes, very much/worst imaginable). Scale from 6-60 with a final seventh question rating patient's overall opinion of scar quality (1-10).

2. Visual Analog Scale (VAS) – Provider Scar Ranking

Digital standardized photographs of scars after complete re-epithelialization is achieved will be assessed by two blinded dermatologists using the VAS. This scale ranges from 0 or normal skin to 10 or worst possible scar taking into account the scar's pigmentation, vascularity, contour, observer comfort, and overall severity. VAS scores of novel biomaterial will be compared to standard SIH.

3. Size of wound

Post-operative wounds will be measured at regularly scheduled follow-ups. The area and volume for each patient's wound will be calculated.

4. Pain score

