3.0 Animal Studies and Previous Human Studies

APIS[®] was FDA cleared in 2019 (FDA number K1827250) for management of full and partial thickness wounds, pressure ulcers, venous stasis ulcers, diabetic ulcers, surface wounds, traumatic wounds, surgical wounds, abrasions, and donor site wounds.

A small case series of 8 patients used APIS[®] in SIH of Mohs surgical wounds on the head and distal lower extremities. Time to complete re-epithelialization was 6 weeks (42 days), suggesting a reduction in healing time compared to standard SIH times for the leg and head of 127 and 57 days, respectively.^{10,11}

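### The primary t-test has no site term, although the trial is built as head and leg groups with very different cited healing times; precision is lost for moderate effects

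*Combined protocol and SAP*

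**What the plan says.** Section 10.0 holds the whole analysis plan. Mean days to complete re-epithelialization "between control and experimental groups will be analyzed with a Student's T-test". One hypothesis follows: "The null hypothesis is that there is no statistically significant difference between control and experimental complete re-epithelialization times". No site term, stratum, covariate or site-specific estimate is named, and the section does not say whether the two sites are pooled.

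Elsewhere, site is part of the design. In Section 2.0 patients "will be randomized into one of four groups", defined by arm and by head or distal lower extremity. Section 6.0 plans 20 patients in each of the four, 80 in total. Section 5.0 specifies 1:1 block randomization but does not say that blocks are formed within site.

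Section 1.0 cites "standard SIH times for the leg and head of 127 and 57 days, respectively". It also singles out the leg: "This provides a useful option to aid SIH in sites like the lower legs, where healing can be prolonged due to intrinsic factors". For the biomaterial, Section 3.0 has one result, from a series of 8 patients and not split by site: "Time to complete re-epithelialization was 6 weeks (42 days), suggesting a reduction in healing time".

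**The concern.** The protocol's own background treats site as a strong influence on the primary endpoint, and the design fixes equal numbers per site, but the planned test uses neither fact. A pooled two-sample test puts the head-leg difference into the error variance, although a balanced design keeps it out of the treatment contrast. Confidence intervals become too wide, and a moderate benefit is more likely to be missed.

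The section also plans no estimate for the lower leg, the site where the background says healing can be slow and the product useful. If separate tests by site were intended, the single null hypothesis has no rule connecting it to two results.

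**Working it through.** **Inputs from the documents.** 20 patients per cell, 40 per arm (Section 6.0); control means of 57 days (head) and 127 days (leg), a gap of 70 days (Section 1.0); biomaterial 42 days (Sections 1.0 and 3.0). The plan states no alpha, power, effect size or standard deviation, so there is no planning calculation to reproduce.

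**Assumptions.** Two-sided 0.05; within-site coefficient of variation (CV) 0.3, 0.5 or 0.7; lognormal times; no dropout; one final test. Section 6.0 allows early completion on significance, which these rates do not cover.

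**Step 1: the estimate.** With 20 per cell, each arm mean is the simple average of its head and leg means. The treatment difference is therefore the same with or without site in the model; only the standard error changes.

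**Step 2: error variance, pooled over site-adjusted.** Let w² = CV² × the mean of the four squared cell means, and gap = leg mean minus head mean within an arm. Then

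ratio = [w² + average over arms of (gap/2)²] / [w² + ((gap in APIS − gap in control)/4)²]

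- No effect, CV 0.3: mean square = (57² + 127²)/2 = 9689; w² = 0.09 × 9689 = 872; (70/2)² = 1225; ratio = (872 + 1225)/872 = 2.40.
- 42 days at both sites, CV 0.3: mean square = (57² + 127² + 42² + 42²)/4 = 5726.5; w² = 515.4; ratio = (515.4 + 612.5)/(515.4 + 306.25) = 1.37.

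| Scenario | Ratio at CV 0.3 / 0.5 / 0.7 |
|---|---|
| No effect | 2.40 / 1.51 / 1.26 |
| 26% reduction at both sites | 2.33 / 1.49 / 1.25 |
| 42 days at both sites | 1.37 / 1.18 / 1.10 |

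The 26% is 1 − 42/57 applied to both sites: 15.0 days (head) and 33.4 days (leg), average (15.0 + 33.4)/2 = 24.2 days.

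**Step 3: simulation.** 40,000 trials per setting, pooled Student t (78 df) against a linear model with arm and site (77 df).

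| Quantity, CV 0.3 / 0.5 / 0.7 | Pooled | With site |
|---|---|---|
| No effect: type I error, % | 0.2 / 1.3 / 2.4 | 4.8 / 5.0 / 4.9 |
| No effect: 95% CI half-width, days | 20.5 / 26.7 / 33.8 | 13.1 / 21.6 / 30.0 |
| 26% reduction: power, % | 87 / 54 / 35 | 99 / 72 / 45 |
| 20% reduction: power, % | 50 / 28 / 19 | 87 / 46 / 27 |
| 42 days at both sites: power, % | >99 | >99 |
| 42 days at both sites: half-width, days | 15.0 / 19.9 / 25.3 | 12.8 / 18.3 / 24.1 |

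A check with normal data, a constant within-site SD and a common 20-day effect agrees: power is 66% against 99% at SD 20, 46% against 84% at SD 30, and 34% against 60% at SD 40.

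**Step 4: weaker conditions, 26% reduction.**

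| Condition, CV 0.3 / 0.5 / 0.7 | Pooled power, % | With site, % |
|---|---|---|
| Control gap halved (57 and 92 days) | 97 / 68 / 43 | 99 / 75 / 48 |
| Control gap 20 days (57 and 77 days) | 99 / 74 / 47 | 99 / 77 / 49 |
| 70-day gap, blocks not formed within site | 76 / 54 / 36 | 99 / 71 / 44 |

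Without blocks within site, the pooled type I error returns to about nominal (5.0 / 5.0 / 4.6%), but power is still lost.

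**Step 5: separate tests by site, 26% reduction.** Power at each site is 88 / 47 / 27%. Counting a win at either site gives 99 / 72 / 47%, but with 9.4 / 9.2 / 9.1% false positives (nominally 1 − 0.95² = 9.75%). Testing each site at 0.025 brings power to 96 / 58 / 32%.

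**The case against.** The strongest reply is that Section 10.0 need not mean a pooled test. Section 6.0 speaks of two experimental and two control groups, so like-for-like t-tests within site fit the wording, and the site gap then leaves the error term. This stands as a reading. It replaces one loss with another, because each test has 20 versus 20 patients and nothing says how two results settle one null hypothesis. The either-site rule costed above is hypothetical; the documents do not propose it.

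Second, the size of the loss rests on assumed CVs and effects, and the 57 and 127 days are outside figures for standard care. That is fair. With a 20-day gap the gain is only a few points at most. If 42 days held at both sites, both tests exceed 99% power. But that figure comes from 8 patients and is not split by site, so it is a weak basis for choosing the analysis.

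Third, the very low pooled type I error requires balanced cells, which Section 5.0 does not guarantee. This is correct, and the conservatism is conditional on that balance. The loss of power is not.

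Finally, an additive site term does not remove all excess variance when the effect differs by site: in the 42-day case at CV 0.3, 306.25 remains beside 515.4. That setting has power to spare.

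**Conclusion.** The concern holds. Read as a single pooled test, the primary analysis ignores a design factor that the protocol's own figures suggest is strongly related to healing time. The harm is lost precision, not bias and not an inflated error rate.

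With the cited 70-day gap, 20 per cell and a uniform 26% reduction, the loss is about 12, 18 and 10 percentage points of power at CV 0.3, 0.5 and 0.7 (99 − 87, 72 − 54, 45 − 35). For a 20% reduction it is 37, 18 and 8 points (87 − 50, 46 − 28, 27 − 19). It falls with a smaller gap and is negligible at the effect the case series would suggest. The pooled test did not outperform the site-adjusted one in any setting tabulated here. The direction is secure; the size depends on the assumed CV, effect and gap. This should be fixed, but it does not make the planned test invalid.

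**What to change.** In Section 10.0, replace the t-test sentence and the null hypothesis with wording such as:

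> The primary comparison is the difference in mean days to complete re-epithelialization between APIS and standard SIH, estimated from a linear model with terms for arm and site (head or distal lower extremity). The single null hypothesis is that this difference is zero. The treatment difference with its 95% confidence interval will also be reported for each site.

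In Sections 2.0 and 5.0, state that 1:1 blocks are formed separately within each site, as the plan of 20 per cell already implies.

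If separate site tests are what the investigators want, Section 10.0 should say so, state which site or combination decides the trial and how the type I error is shared, and acknowledge the 20-versus-20 comparison.

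The cost is a few sentences, one allocation list per site and one degree of freedom (77 instead of 78). No patients, visits or measurements are added.

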1.0 Background

Brief Summary:

The purpose of this study is to elucidate if a novel biomaterial containing gelatin, manuka honey, and hydroxyapatite enhances secondary intention healing when compared to conventional secondary intention healing for surgical defects after Mohs micrographic surgery on the head and distal lower extremities (below the knee).

Detailed Description:

Secondary intention healing (SIH) is often underutilized and has several advantages compared to primary surgical repair.^{1,2} Wound care is minimal, bleeding and infection are rare, and risks associated with primary closure (e.g. hematoma, suture granuloma, graft or flap failure) are non-existent.³ Importantly, SIH facilitates surveillance of tumor recurrence, whereas flaps and grafts may bury residual tumor.^{1,3} When used in appropriate anatomical locations, SIH leads to high patient satisfaction.^{1,2,4} However, SIH requires regular wound care that can be cumbersome to patients.^{3,5}

Prior studies utilizing biologic dressings have shown patients report better quality of life during the post-operative period related to less pain, decreased dressing changes, and faster healing times.^{5,6} Biologic dressings provide an alternative to surgical autografts and eliminate the risks associated with graft harvesting (e.g. pain, infection, and scarring).^{5,7} For many patients, the cosmetic outcome following healing is important. However, cosmetic outcome with SIH is variable and depends on many factors, namely location (e.g. concavities favorable), skin laxity, and underlying musculature.^{1,2,8} Exuberant granulation tissue, hypopigmented and telangiectatic scars are the most frequent adverse cosmetic outcomes with SIH.^{3,9}

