5.0 Enrollment/Randomization

Patient enrollment will occur at Vanderbilt University Medical Center One Hundred Oaks Department of Dermatology Mohs Surgical Unit. All patients eligible for study may be considered. Patients with Mohs surgical defects on the head and distal lower extremities amenable and conducive for SIH will be randomized to intervention or control by block randomization. Subjects will be randomized in a 1:1 ratio.

Address of enrollment: Vanderbilt Dermatology One Hundred Oaks [name] [contact]

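### The scar outcomes are compared by an unadjusted t-test although the protocol names wound location as a determinant of the cosmetic result; a prespecified location term would be a cheap gain in precision

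*Combined protocol and SAP*

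**What the plan says.** Section 10.0 is the whole statistical plan. Mean days to re-epithelialisation "between control and experimental groups will be analyzed with a Student's T-test". For the scar scores it adds only: "Secondary outcomes of patient and observer cosmetic outcome will be compared similarly". No covariate, stratum or model is named anywhere, so the second sentence can refer only to the t-test. The section does not say whether head and leg are pooled or tested separately.

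Section 1.0 says that "cosmetic outcome with SIH is variable and depends on many factors, namely location (e.g. concavities favorable), skin laxity, and underlying musculature".

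The design separates location at one level only. Section 2.0 lists the groups as "standard SIH or biomaterial APIS[®] enhanced SIH on the head or distal lower extremities", and section 6.0 plans 20 patients per arm at each of the two sites. Under section 5.0 patients "will be randomized to intervention or control by block randomization", and "Subjects will be randomized in a 1:1 ratio"; no balancing by head subsite is mentioned. Under the Day 0 procedures in section 6.0, "Pre and postoperative photos will be obtained and stored in the Electronic Medical Record and Vanderbilt HIPAA compliant Box".

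**The concern.** Better cosmetic outcome is one of three aims in section 2.0. It is measured by the POSAS patient scale and by a 0 to 10 VAS scored by two blinded dermatologists. Section 4.0 admits head wounds without restriction on concavity, so 20 against 20 head wounds may mix concave sites with convex or flat ones. If concavity matters as section 1.0 says, two things follow. Differences between subsites go into the error term and widen the confidence interval. And if one arm happens to receive more concave wounds, that difference stays in the estimated treatment effect. A head/leg term alone would not deal with either, because concavity varies within the head. The photographs needed to code it are already part of the plan.

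**Working it through.** **No figure to reproduce.** The plan gives no alpha, power, effect size, SD or subsite mix.

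**Inputs from the documents:** 20 wounds per arm per site; unadjusted t-test; VAS 0 to 10.

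**Assumed inputs:** two-sided 5% test; true treatment effect 1 VAS point; within-location SD s = 1.5 or 2.0; half of head wounds concave; concave wounds better by D = 1, 2 or 3 points; leg wounds scored like convex ones.

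**1. Power, both sites pooled (40 v 40).** Simulation of VAS = 5 − D × concave − 1 × APIS + N(0, s), 6,000 trials per setting:

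| s | D | t-test | treatment + head/leg | treatment + three-level location | gain from subsite alone |
|---|---|---|---|---|---|
| 1.5 | 1 | 81% | 82% | 84% | 2 |
| 1.5 | 2 | 73% | 76% | 83% | 7 |
| 1.5 | 3 | 62% | 68% | 83% | 15 |
| 2.0 | 1 | 57% | 58% | 59% | 1 |
| 2.0 | 2 | 53% | 55% | 59% | 4 |
| 2.0 | 3 | 44% | 48% | 58% | 10 |

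A repeat run gave 67% v 83% in the third row, a gain of 16 points, so the range is about 1 to 16.

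Hand check for s = 1.5, D = 2. Residual variances:
- t-test: 2.25 + 4 × 0.25 × 0.75 = 3.00
- head/leg: 2.25 + ½ × 4 × 0.5 × 0.5 = 2.75
- three-level: 2.25

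SE = √(2V/40) = 0.387, 0.371 and 0.335. A 1-point effect is then 2.58, 2.70 and 2.98 standard errors, giving power of about 72%, 76% and 84% by the noncentral t. This agrees with the table.

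**2. Precision within the head alone (20 v 20).** Let R² be the assumed share of scar-score variance explained by subsite. The residual SD becomes SD × √(1 − R²). The difference detectable with 80% power falls from 0.91 SD unadjusted to 0.89 (R² 0.05), 0.86 (0.10), 0.81 (0.20), 0.76 (0.30) or 0.71 SD (0.40).

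**3. Chance imbalance.** The exact difference of two Binomial(20, p) counts gives the probability of a gap of at least 4 of 20 (20 percentage points): 23% for p = 0.3, 26% for 0.4, 27% for 0.5, 16% for 0.8 and 6% for 0.9.

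**4. Effect of that imbalance on the VAS difference.** With D = 2, the head shift is 0.20 × 2 = 0.4 points. Head wounds are half of the pooled sample, so the pooled shift is 0.4 × 20/40 = 0.2 points. In relative terms, for a 12 v 8 split with p = 0.5, the subsite gap is √(R²/0.25) in SD units and the head SE is √(2/20) = 0.316 SD:
- R² 0.10: gap 0.632, shift 0.13 SD = 0.40 SE
- R² 0.20: gap 0.894, shift 0.18 SD = 0.57 SE
- R² 0.30: gap 1.095, shift 0.22 SD = 0.69 SE

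**5. Type I error.** Simulation (200,000 trials, 20 v 20, R² 0.10 to 0.30) gives about 5% averaged over randomisations, and 5.6% to 6.3% given a 12 v 8 split.

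**The case against.** The strongest reply is that nothing here is an error. An unadjusted t-test on randomised arms is valid, its standard error already allows for chance imbalance, and the outcomes are secondary. That stands: step 5 shows the overall error rate at its nominal level and only slightly raised given a marked imbalance. A reader might infer that the planned test is biased or invalid; the documents and the calculation do not support that.

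Three further limits also stand.

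- **Size.** It is wholly assumed, since section 1.0 gives a direction for concavity but no magnitude. Sections 4.0 and 5.0 enrol only defects suitable for secondary intention healing, which may narrow the mix of sites. A 50% concave share is the least favourable case for imbalance.
- **Attribution.** It is tempting to credit subsite with the whole gap between the t-test and the three-level model (up to 21 points in the table). Part of it comes from the head/leg term, because the simulation sets leg wounds equal to convex head wounds. Likewise the 0.4-point shift belongs to the head comparison, not the pooled one.
- **POSAS.** A reader might carry the VAS figures over to it. The patient score includes pain and itch, and the documents do not say that concavity affects either.

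Location is also only one of the factors in section 1.0; skin laxity and musculature would remain unadjusted. None of this removes the point that the analysis ignores a determinant that the protocol itself names and could use at little cost.

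**Conclusion.** The concern holds as a matter of precision and credibility, and is best labelled a cheap improvement. The gain from subsite could be substantial if the gap between subsites is large against the within-location SD, and is close to nil if it is small. The result does not depend on whether section 10.0 means a pooled or a per-site test: step 1 covers the first and step 2 the second. Prespecification is what matters most. If an imbalance in head sites is noticed after the scar scores are seen, an adjustment added then would look like a choice made on the results.

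**What to change.** Replace the last sentence of section 10.0 with:

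> Observer VAS and POSAS patient score will be compared between arms by a linear model with treatment and wound location (head concave; head convex or flat; distal lower extremity), with head subsite coded from the pre-operative Day 0 photographs by an existing team member unaware of the arm, before scar scores are examined. The adjusted difference with 95% CI is the result; it will also be shown separately for head (adjusted for subsite) and distal lower extremity, and the unadjusted t-test is a sensitivity analysis.

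Cost: one sentence, the coding of about 40 head wounds from photographs already planned, and two degrees of freedom (78 to 76). No visits, patients or assessors are added. Downsides: the concave v convex or flat coding is a judgement; the pooled estimate assumes one treatment effect for head and leg, which is why the separate results are shown; and the effort buys almost nothing if subsite matters little.
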